Measure	Day -28 to First Treatment	D1	D2	D8	D15	D22	D29	D43	D43-50	D57	D71	D85	Until Progression	Discontinuation/ Last Treatment	(+/- 2 weeks) after Last Treatment	Every 12 weeks (+/- 2 weeks)
Written informed consent	X					X										
Inclusion/exclusion criteria	X	X														
Medical history	X															
Cancer disease history	X															
Prior anticancer drug/radiotherapy/ procedures	X															
Other prior medications	X															
Demographic data	X															
HBV, HCV, and HIV testing	X															
Ophthalmology examination including slit lamp evaluation inclusive of the anterior segment and with visual acuity	X															
Physical examination ^{t,x}	X	X	X	X	X	X	X	X		X	X	X	6-weekly ^u	x/X	X	

Table 1	Schedul	e of	Asse	ssme	ents:	Dos	e Es	calati	ion Pa	rt						
	Screening Assessments						Т	Discontinuation/ End-of- Treatment Visits ^w	Safety Follow-up Visit ^w	Long-Term Follow-up ^b						
		V1	V2	V3	V4	V5	V6	V7	V7	V8	V9	V10		Up to 7/28 Days (+/- 5 days) after		
	Day -28 to	W1 D1	W1 D2	W2 D8	W3 D15	W4 D22	W5	W7 D43	W7 D43-50	W9 D57	W11	W13 D85		Decision of Discontinuation/	10 Weeks (+/- 2 weeks)	
Measure	First Treatment	DI	D2	ръ	D15	DZZ	D29	D43	D43-50	ופע	D71	ספת	Until Progression	Last Treatment	after Last Treatment	Every 12 weeks (+/- 2 weeks)
Dermatological assessment ^e	X				X		X	X		X	X	X	6-weekly up to/including Week 25, then every 12 weeks	x/X	X	
SpO ₂	X	X			X		X	X		X	X	X	2-weekly	X	X	
12 lead ECG ^f	X	X/X	X	X	X/X		X	X				X	6-weekly normal ECGs ^u	-/X	X	
Vital signs including weight and height (height at screening only) ^g	X	X	X	X	X	X	X	X	X	X	X	X	2-weekly	x/X	X	
ECOG PSh	X	X	X	X	X		X	X		X	X	X	2-weekly	x/X	X	
Enrollment (if eligible)i	X															
Hematology/ hemostaseology ^j	X	X	X	X	X	X	X	X		X	X	X	2-weekly	x/X	X	
Core serum chemistry ^k		X	X	X		X	X			X	X		2-weekly			
Full serum chemistryk	X				X			X				X	6-weekly	x/X	X	
Serum electrophoresis	X											X		-/X		
Urinalysis ^l	X				X			X				X	6-weekly ^u	x/X	X	
β-HCG pregnancy test (if applicable) ^m	X	X					X			X		X	4-weekly	-/X	X	
FSH (if applicable)	X															

Table 1	Schedul	e of	Asse	ssme	ents:	Dos	se Es	calat	ion Pai	rt						
	Screening Assessments						_		ent Part days) ^a					Discontinuation/ End-of- Treatment Visits ^w	Safety Follow-up Visit ^w	Long-Term Follow-up ^b
		V1	V2	V3	V4	V5	V6	V7	V7	V8	V9	V10		Up to 7/28 Days		
		W1	W1	W2	W3	W4	W5	W 7	W 7	W9	W11	W13	1	(+/- 5 days) after Decision of	10 Weeks	

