- and 120 ± 10 minutes after the end of the infusion. If the re-initiated subject does not have an infusion-related reaction during the first infusion the vital sign assessments at 30 ± 5 , 60 ± 10 , and 120 ± 10 minutes after the end of the infusion may be waived for subsequent infusions.
- h If the Screening ECOG PS was performed within 3 days prior to Cycle 1 Day 1, it does not have to be repeated at Cycle 1 Day 1.
- i Enrollment will be done after the confirmation of fulfilling all Screening inclusion criteria without matching any exclusion criterion. In the case of new clinical laboratory abnormalities detected prior to the first dose, the eligibility of the subject should be reconsidered with the guidance of Medical Monitor.
- j Hematology (including complete blood count) and hemostaseology assessments are detailed in Table 8. Follicle-stimulating hormone at Screening, if applicable. Complete blood count results must also be drawn and reviewed within 48 hours prior to dose administration. For subjects experiencing signs of anemia including, but not limited to, a significant drop in Hgb value (especially Hgb < 8 g/dL), routine monitoring of Hgb, red blood cells, and hematocrit should be performed weekly.
- k Full chemistry (which includes core chemistry) and core serum chemistry samples are detailed in Table 8. Samples for core chemistry results must be drawn and reviewed within 48 hours prior to dose administration.
- 1 A full urinalysis is required at Screening and the End-of-Treatment visit and basic urinalysis at each visit indicated prior to administration of study drug. If urinalysis (full or basic) is positive for protein, sediment will be evaluated.
- m β-HCG must be determined from serum at Screening and from either urine or serum sample thereafter. Results of the most recent pregnancy test should be available prior to next dosing. Pregnancy testing is applied for women of childbearing potential. Woman are considered of childbearing potential unless they are postmenopausal (defined by continuous amenorrhea excluding the amenorrhea caused by the administration of anticancer therapy) for at least 12 months, are surgically sterile or have increased FSH levels indicating menopause.

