- j Hematology (including complete blood count) and hemostaseology assessments are detailed in Table 8. Follicle-stimulating hormone at Screening, if applicable. Complete blood count results must also be drawn and reviewed within 48 hours prior to dose administration according to the schedule in the above table. For subjects experiencing signs of anemia including, but not limited to, a significant drop in Hgb value (especially Hgb < 8 g/dL), routine monitoring of Hgb, red blood cells, and hematocrit should be performed weekly.
- k Full chemistry (which includes core chemistry) and core serum chemistry samples are detailed in Table 8. Samples for core chemistry results must be drawn and reviewed within 48 hours prior to dose administration according to the schedule in the above table.
- 1 A full urinalysis is required at Screening and the End-of-Treatment visit and basic urinalysis at each visit indicated prior to administration of trial drug. If urinalysis (full or basic) is positive for protein, sediment will be evaluated.
- m β-HCG must be determined from serum at Screening and from either urine or serum sample thereafter. Results of the most recent pregnancy test should be available prior to next dosing. Pregnancy testing is applied for women of childbearing potential. Woman are considered of childbearing potential unless they are postmenopausal (defined by continuous amenorrhea excluding the amenorrhea caused by the administration of anticancer therapy) for at least 12 months, are surgically sterile or have increased FSH levels

Serum VCA-IgG Ab and EBNA IgG examination should be done for gastric cancer cohort.

In order to mitigate potential infusion-related reactions, all subjects must receive premedication with an antihistamine and with paracetamol (acetaminophen) approximately 30 to 60 minutes prior to each dose of MSB0011359C (eg, 25-50 mg diphenhydramine and 500-650 mg paracetamol [acetaminophen] intravenous or oral equivalent) for the first 2 infusions. Premedication is optional and at the discretion of the Investigator after the second infusion. If Grade 2 infusion reactions are seen during the first two infusions, then premedication should not be stopped. Steroids as premedication are not permitted. MSB0011359C should be administered according to the dose decided from the dose escalation part of the trial by intravenous infusion over 1 hour (-10 minutes/+20 minutes, ie, over 50 to 80 minutes).

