3.4.6 Embryofetal Toxicity

Embryofetal toxicities are a known risk of the PD-1/PD-L1 targeting class. Animal models link the PD-1/PD-L1 signaling pathway with maintenance of pregnancy through induction of maternal immune tolerance to fetal tissue. Based on its mechanism of action (MoA), MSB0011359C may cause fetal harm when administered to a pregnant female and conferred as an important potential risk. An appropriate contraception warning is provided in this clinical protocol. Subjects with pregnancy or in lactation period are prohibited from enrolling in clinical trials.

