During Screening, a serum β -human chorionic gonadotropin (β -HCG) pregnancy test will be performed for females of child bearing potential and blood HBV, HCV and HIV testing will be performed for all Screening subjects as these conditions are trial entry exclusion criteria. Females who are postmenopausal (age-related amenorrhea \geq 12 consecutive months and if needed increased FSH > 40 mIU/mL [in the postmenopausal range]), or who have undergone hysterectomy or bilateral oophorectomy are exempt from pregnancy testing. If necessary to confirm postmenopausal status, an FSH will be drawn at Screening. Serum VCA-IgG Ab and EBNA IgG examination will done in the GC expansion cohort.

• The tumor evaluation (type/staging, etc.) will be performed using CT scan or MRI (if MRI is used, CT of chest is mandatory) as well as tumor markers or any other established methods (see Section 7.2.5 for details). Brain CT/MRI scan (either, with contrast preferred) is required if not performed within the previous 6 weeks. Bone scans should be performed as clinically indicated.

Collection of tumor tissues or archived surgical specimen will also be done during this period, if applicable (optional for the dose escalation part). Subjects in the expansion cohorts are required to provide tumor tissue samples, see Section 5.3.1 and Section 7.6.1.3 for details.

For subjects in the GC, ESCC, and BTC expansion cohorts only, patient-reported outcome questionnaires (PGIS, EORTC QLQ-C30, EORTC QLQ-BIL21, EORTC QLQ-HCC18, EORTC QLQ-OES18, and EORTC QLQ-STO22) will be administered and completed by the subjects at Screening to collect baseline data about their symptom severity.

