- Serum electrophoresis at Week 13 (Visit 10).
- A basic urinalysis will be performed prior to trial treatment as detailed in Table 1.
- A serum β-HCG pregnancy test will be required at Screening, urine or serum β-HCG pregnancy test will be performed prior to each administration of the study drug every 4 weeks (if applicable). If necessary to confirm postmenopausal status, an FSH will be drawn at Screening.
- The tumor evaluation (see Section 7.3) will be performed at Week 7, and then once every 6 weeks, with a tumor assessment visiting time window of 5 days prior to dosing.
- PK samples will be drawn as detailed in Table 3.
- Free T4 and TSH will be measured prior to trial treatment according to Table 1.
- ADA samples will be drawn as detailed in Table 3. The term for ADA on the CRF is human antihuman antibodies (HAHA)
- Soluble factors will be drawn as detailed in Table 3 and as described in Section 7.6.1.2.
- Samples for TGFβ determination will be drawn as detailed in Table 3.
- Blood samples for gene expression evaluation will be collected according to Table 3 (prior to IMP administration where applicable).

CONFIDENTIAL INFORMATION

• For subjects undergoing the optional Week 7 biopsy, the biopsy should be performed within 7 days after the Week 7 IMP administration (Table 3).

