7.4.4 Vital Signs, Physical Examinations, and Other Assessments

The ECOG PS will be assessed at Screening and at subsequent visits as indicated in the Schedules of Assessments (Table 1 and Table 2) and documented in the eCRF.

Body weight will be measured at Screening and at subsequent visits as indicated in the Schedules of Assessments (Table 1 and Table 2) and documented in the eCRF. Body height will be measured at Screening only.

A physical examination will be conducted and SpO₂ measured at Screening and at subsequent visits as indicated in the Schedules of Assessments (Table 1 and Table 2) and documented in the eCRF (detailed description in Section 7.1). Any abnormalities arising or worsening after the signing of the ICF should be documented in the eCRF Adverse Event section (see Section 7.4.1). Abnormal findings are to be reassessed at subsequent visits.

An ophthalmology examination including slit lamp evaluation inclusive of the anterior segment and with visual acuity should be conducted at Screening. At subsequent visits, eye signs and symptoms should be checked. If there are any clinically relevant findings, then an appropriate ophthalmology examination including slit lamp evaluation inclusive of the anterior segment and with visual acuity should be obtained within 2 days.

Digital 12-lead ECGs will be recorded at Screening and at trial visits as indicated in the Schedules of Assessments (Table 1 and Table 2) until Week 13 (Visit 10).

All newly diagnosed or worsening conditions, signs and symptoms observed since Screening, whether related to trial treatment or not, are to be reported as AEs.

For female subjects of childbearing potential, serum β -HCG pregnancy test will be carried out during the Screening period. A urine or serum β -HCG test will be performed once a month during the treatment period as indicated in the Schedules of Assessments (Table 1 and Table 2), at the End-of-Treatment visit, and at the Safety Follow-up visit. Results of the most recent pregnancy test should be available prior to the next dosing of IMP. Subjects who are postmenopausal (age-related amenorrhea \geq 12 consecutive months and if needed FSH > 40 mIU/mL [in the postmenopausal range] as outlined in Section 7.1.1), or who have undergone hysterectomy or bilateral oophorectomy are exempt from pregnancy testing. If necessary to confirm postmenopausal status, an FSH will be drawn at Screening.

CONFIDENTIAL INFORMATION

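### The schedule footnotes let raised FSH alone exempt a woman from pregnancy testing, while Sections 7.1.1 and 7.4.4 use FSH only to confirm 12 months of amenorrhea

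*Protocol*

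**What the plan says.** Table 1 footnote m applies pregnancy testing to women of childbearing potential and gives the protocol's only explicit definition of that status. Its first ground for leaving the group is continuous amenorrhea, not counting amenorrhea caused by anticancer therapy, and the list ends "for at least 12 months, are surgically sterile or have increased FSH levels indicating menopause". Table 2 footnote m, for the expansion part, runs to "for at least 12 months, are surgically sterile or have increased FSH levels", where the available text breaks off.

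Section 7.1.1 exempts a woman with age-related amenorrhea of at least 12 "consecutive months and if needed increased FSH > 40 mIU/mL [in the postmenopausal range]), or who have undergone hysterectomy or bilateral oophorectomy". Section 7.4.4 repeats the 12-month amenorrhea requirement, with "if needed FSH > 40 mIU/mL [in the postmenopausal range] as outlined in Section 7.1.1), or who have undergone hysterectomy or bilateral oophorectomy". The purpose of the FSH draw is stated in Sections 7.1.1, 7.1.2.1, 7.1.2.2 and 7.4.4: "If necessary to confirm postmenopausal status, an FSH will be drawn at Screening".

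The pregnancy-test row of Table 1 has Screening, Days 1, 29, 57 and 85, then every 4 weeks, End-of-Treatment and Safety Follow-up. Inclusion criteria #10 (escalation) and #12 (expansion) and deviation PDEV12 in SAP Appendix 1 use the term childbearing potential without defining it.

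**The concern.** The two rules give different answers for one kind of patient: raised FSH, less than 12 months of amenorrhea, no sterilising surgery. A site working from the visit schedule would drop her on-treatment tests; a site working from the body text would do them.

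The tests matter because Section 3.4.6 states that "MSB0011359C may cause fetal harm when administered to a pregnant female and conferred as an important potential risk". Footnote m asks that "Results of the most recent pregnancy test should be available prior to next dosing", and Section 7.4.2 requires dosing to stop at once if a subject becomes pregnant. For this woman no scheduled on-treatment test would trigger either safeguard.

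Footnote m also undercuts its own caution. Its first ground refuses to count amenorrhea caused by anticancer therapy, but its FSH ground carries no such exclusion. Earlier systemic treatment is expected in this trial; the biliary tract cohort, for example, is second line.

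**Working it through.** The plan states no figure here. The check compares the two rules and then counts the tests at stake.

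**The rules side by side**

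| | Table 1 footnote m | Sections 7.1.1 and 7.4.4 |
|---|---|---|
| Amenorrhea | At least 12 months, not therapy-caused | At least 12 consecutive months, age-related |
| FSH | Separate ground, joined by *or*, no duration attached | Above 40 mIU/mL, if needed, added to the amenorrhea criterion |
| Surgery | Surgically sterile | Hysterectomy or bilateral oophorectomy |

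As logic, the footnote exempts on (12 months) OR (surgically sterile) OR (raised FSH). The text exempts on (12 months, with FSH if needed) OR (named surgery). Raised FSH with under 12 months of amenorrhea and no surgery satisfies the first rule and fails the second. The surgery row is a second, separate difference.

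**Tests omitted.** Inputs: the Table 1 test row, two-weekly dosing, End-of-Treatment 28 days and Safety Follow-up 10 weeks after the last dose. Screening is not counted, because FSH is itself drawn at Screening and would rarely cancel that test. Visits are taken as on time.

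- One dose: Day 1, plus 2 post-treatment tests = 3.
- Last dose at Week 7 (Day 43): Days 1 and 29, plus 2 = 4.

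Both counts hold provided she does not reach 12 months of amenorrhea meanwhile. On longer treatment that point matters, because from then on she is exempt under both rules and the discrepancy ends.

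- 6 months of amenorrhea at Day 1: 12 months is reached about 183 days later. Days 1, 29, ..., 169 give (169 − 1)/28 + 1 = 7.
- 0 months at Day 1, 12 months of treatment (26 doses, last on Day 1 + 25 × 14 = 351): Days 1, 29, ..., 337 give (337 − 1)/28 + 1 = 13. End-of-Treatment falls at about Day 351 + 28 = 379, past the 12-month mark, so it is not added.
- 0 months at Day 1, 24 months of treatment: Days 1, 29, ..., 365 give (365 − 1)/28 + 1 = 14.

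Section 7.1.2 lets a Screening procedure done within 3 days stand in for the Day 1 assessment. If that is applied to the pregnancy test, each count is one lower: 2, 3, 6, 12 and 13.

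**The case against.** The best defence is that the footnote should be read with the body text. It speaks of FSH levels that indicate menopause, the body supplies the cut-off, FSH is scheduled only at Screening, and its stated purpose is to confirm postmenopausal status. On that reading nobody exempts a woman who is still menstruating. This works for the cut-off: the footnote can borrow 40 mIU/mL from Section 7.1.1, so the missing number is not the defect. It does not work for the duration. The footnote already lists postmenopausal status as its own ground, so a further FSH ground can only matter for women who do not meet the 12-month criterion. Nothing else in the protocol or SAP reconciles the two.

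Other points on that side stand:

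- Sections 7.1.1 and 7.4.4 list who is exempt without saying that nobody else is. That this woman must be tested follows by implication only.
- Contraception is still required where conception is possible, and suspected pregnancy must be reported at once. The note to the contraception criteria (#9 and #11) does rely on the same undefined term.
- Table 2 footnote m is legible only in part, so a qualifier after the break cannot be excluded. Only Table 1 is fully verified.
- SAP Section 4 gives 24 August 2017 as the last participant's start. Rewording the inclusion criteria changes no first-time enrolment.

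A reader might also infer a much larger loss by running the schedule forward without a stop: 13 + 2 = 15 tests over 12 months, 28 over 24 months ((701 − 1)/28 + 1 = 26, plus 2), or 15 + 15 = 30 with one re-initiated year. The documents do not support these as typical. They apply only if 12 months of qualifying amenorrhea is never completed (recurrent bleeding or therapy-caused amenorrhea) or her status is not reassessed. Recurrent bleeding sits poorly with FSH that indicates menopause, and SAP Section 9.15 records no re-initiation at its cut-off.

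**Conclusion.** The inconsistency is real in Table 1 and appears to extend to Table 2. Followed as written, the schedule omits scheduled tests after Screening for women with raised FSH and short amenorrhea: 3 or 4 on short treatment, about 7 or 13 to 14 on longer treatment depending on amenorrhea at Day 1. These counts assume on-time visits, continuing amenorrhea of a qualifying kind, and recognition of the date on which 12 months is reached.

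The number of women concerned is not given and is probably small. It would go too far to conclude that eligibility screening fails or that the trial's results are affected: the Screening test would rarely be lost, and no endpoint, sample size or analysis depends on this rule. It is a minor safety-conduct correction.

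**What to change.** In footnote m of Tables 1 and 2, remove FSH as a separate ground. Suggested wording: *Women are of childbearing potential unless they are postmenopausal (age-related amenorrhea of at least 12 consecutive months not caused by anticancer therapy, confirmed if needed by FSH > 40 mIU/mL) or surgically sterile. Raised FSH without 12 months of amenorrhea does not exempt from pregnancy testing.* Refer to this definition in inclusion criteria #10 and #12, and use it when reviewing PDEV12, which is its main use for women already enrolled.

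This wording leaves the surgical ground as it is. If that ground is also aligned with Sections 7.1.1 and 7.4.4, declare it as a second change. A woman with tubal sterilisation arguably counts as surgically sterile under the footnote but is not exempt under the text, and Appendix 2 lists bilateral tubal occlusion as a contraceptive method. Aligning would add testing for such women.

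The cost is wording in two footnotes and two criteria, plus the urine or serum tests counted above for each affected woman still to be treated.

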2.1 Investigational Sites

Dose escalation part: The trial will be conducted in up to 2 sites in Japan.

Expansion part: The trial will be conducted in up to 30 sites in Japan, Korea and Taiwan.

2.2 Trial Coordination/Monitoring

The Sponsor will coordinate the trial and will provide the support of CROs for some activities of the trial. Sponsor functional groups will perform oversight of the activities performed by the CROs.

The Sponsor will supply the trial medication of MSB0011359C to the sites. Packaging and distribution of clinical supplies will be performed by the Clinical Trial Supplies department of the Sponsor and the contracted manufacturing organization.

Safety laboratory assessments will be performed locally by investigational sites. Pharmacokinetics (PK), cc assessments will be performed centrally under the responsibility of the Sponsor.

The Global Drug Safety Department, Merck KGaA, Darmstadt, Germany or their designated representatives will assure drug safety monitoring, pharmacovigilance, and the timely reporting of adverse events (AEs) and serious AEs (SAEs).

Quality assurance of the trial conduct will be performed by the Development Quality Assurance Department, Merck KGaA, Darmstadt, Germany.

CONFIDENTIAL INFORMATION

The department of Global Biostatistics will supervise the statistical analyses (with the exception of the PK data analyses) which will be outsourced to a CRO.

The Coordinating Investigator, CCI represents all investigators for decisions and discussions regarding this trial, consistent with the International Council for Harmonisation (ICH) Topic E6 Good Clinical Practice (GCP), hereafter referred to as ICH GCP. The Coordinating Investigator will provide expert medical input and advice relating to trial design and execution and is responsible for the review and signoff of the clinical trial report.

Signature pages for the Protocol Lead and the Coordinating Investigator, as well as a list of Sponsor responsible persons, are in Appendix 4.

2.2.1 Safety Monitoring Committee

To ensure subjects' safety during the dose escalation and expansion parts of the trial, a Safety Monitoring Committee (SMC) will review the safety data on a regular basis. The SMC consists of permanent members from the Sponsor and/or CRO (at least the Medical Responsible, the Global Drug Safety Product Leader, and the Biostatistician for the expansion part), the Coordinating Investigator, and an external expert with expertise in the management of cancer patients. The SMC will evaluate the safety data from the dose levels 1 and 3 mg/kg and PK data from the dose level 1 mg/kg of EMR200647-001 as well before Study EMR200647-008 will be started at the 3 mg/kg dose level. During the dose escalation part of the trial, the SMC will evaluate the safety information of all the treated subjects, including those who started the treatment but did not complete the dose-limiting toxicity (DLT) evaluation period, and available PK data and will decide on the DLTs relevant for the treatment and will decide by consensus on dose escalation or suspension of enrollment and/or declaration of the maximum tolerated dose (MTD), with the final adjudication being a Sponsor prerogative. Treatment-related adverse events leading to a delay in dosing will be considered as well for the decision to go to the next dose level.

The SMC will recommend an MSB0011359C dose for the expansion part of the trial and may consider the MTD plus overall AEs, PK and any supporting information such as biomarker data. During the expansion part of the trial, the SMC will monitor on an ongoing basis (eg, when 15 subjects have been enrolled and treated for at least 4 weeks), all safety information of the participating subjects and will decide by consensus on continuation, modification, or suspension of the trial or of a particular expansion cohort. The SMC may modify the frequency of meetings as deemed appropriate by the SMC during the course of the trial. The specific working procedures will be described in an SMC charter, which will be established prior to the start of recruitment.

